2.15. Sample size calculation and data analysis plan

Sample size estimates have been developed to test the study's primary question related to whether the Virtual Advisor intervention is no worse than the intervention delivered by trained human advisors, i.e., a test of non-inferiority.⁶³ Using a two-tailed 95% confidence interval on the effect size (Cohen's d), the threshold of clinical significance between the two treatments, Δ , has been developed to demonstrate clinical noninferiority of the new intervention (Virtual Advisor) if the confidence interval lay completely above $-\Delta$, while clinical noninferiority of the Peer Advisor intervention will be demonstrated if the confidence interval lay completely below $+\Delta$. In this trial, the effect size (Cohen's d) is the standardized difference between the change in walking minutes/week over the 12-month intervention period. The critical value of Δ is based on a clinically meaningful difference between arms of 30 minutes of walking per week,³ and a within-arm standard deviation of 90, accounting for clustering within centers.⁶⁴ The noninferiority margin was based on a clinically meaningful difference, in one direction, between arms of 30 minutes walking/week,³ and a within-arm standard deviation of 90, accounting for clustering within centers ($\Delta=.30$).⁶⁴

We calculated that a sample of 112 per arm (224 total) would provide 80% power to demonstrate noninferiority between the two interventions using a simple pre-post analysis. We plan to use a mixed-effects linear regression model. Mixed-effects linear regression effectively addresses both missing data and early dropout in "intent-to-treat" analysis.^{65,66} In addition, the multiple assessment time points in the trial (at baseline, 6 months, and 12 months) will serve to provide more detailed information on changes over time relative to studies using pre-post assessment only.⁶⁷ Twenty-one additional participants were recruited to protect against loss to follow-up. Similar mixed-effects

linear regression techniques will be used to address the secondary outcomes of interest, e.g., intervention impacts on well-being variables across the study period.

3. Results

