Other	3	1.2	2	1.6	1	0.8	
Missing	3	1.2	3	2.4	0	0.0	
Marital status							
Married or living with partner	125	51.0	59	48.0	66	54.1	0.11
Not married or living with partner	118	48.2	63	51.2	55	45.1	
Refused	2	0.8	1	0.8	1	0.8	
Education							
Less than High School	62	25.3	27	21.9	35	28.7	0.42
High school	45	18.4	28	22.8	17	13.9	
Some college	80	32.7	39	31.7	41	33.6	
College	27	11.0	15	12.2	12	9.8	
Postgraduate	28	11.4	12	9.8	16	13.1	
Missing	3	1.2	2	1.6	1	0.8	
Household income							
< \$5000 to \$34,999	32	13.1	17	13.8	15	12.3	0.97
\$35,000 to \$49,999	23	9.4	11	8.9	12	9.8	
\$50,000 to \$74,999	30	12.2	16	13.0	14	11.5	
\$75,000 or greater	45	18.4	21	17.1	24	19.7	
Don't know, refused, missing	115	46.9	58	47.2	57	46.7	
Variable (continuous)	Mean	SD	Mean	SD	Mean	SD	
Age (yr.)	62.3	8.4	63.1	8.3	62.4	8.5	0.82
Years in US	47.4	17.0	47.7	17.2	47.1	16.8	0.80
Number in household	3.5	2.2	3.7	2.5	3.3	1.8	0.16
CHAMPS Q – baseline (min/wk.):							
Walking for exercise & leisure	45.9	91.6	48.0	98.1	43.6	81.4	0.71
Walking briskly	3.7	16.1	5.1	19.7	2.3	11.4	0.18

Moderate, vigorous activities	23.5	69.2	22.4	62.8	24.6	75.1	0.81
-------------------------------	------	------	------	------	------	------	------

Fig. 1. Screenshot of the Virtual Advisor (“Carmen”).

References:

1. IM, Shiroma EJ, Lobelo F, et al. Effect of physical inactivity on major non-communicable diseases worldwide: an analysis of burden of disease and life expectancy. *Lancet*. 2012;380(9838):219-229.
3. Physical Activity Guidelines Advisory Committee. *Report of the Physical Activity Guidelines Advisory Committee, 2008*. Washington, DC: U.S. Department of Health and Human Services;2008.
6. Silvia CA. Barriers to physical activity in the Hispanic community. *J Public Health Policy*. 2003;24(1):41-58.

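### The margin is justified as 30 walking minutes per week but tested on Cohen's d; if d is divided by the observed SD, the deficit tolerated in minutes moves with that SD

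*Combined protocol and SAP*

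**What the plan says.** All of the relevant text is in section 2.15. The question is "whether the Virtual Advisor intervention is no worse than the intervention delivered by trained human advisors, i.e., a test of non-inferiority". The clinical basis is in minutes: "The noninferiority margin was based on a clinically meaningful difference, in one direction, between arms of 30 minutes walking/week". The planning SD within arm is 90, described as already accounting for clustering within centers, and Δ is printed as .30.

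The decision is on another scale. A two-tailed 95% confidence interval for Cohen's d is used "to demonstrate clinical noninferiority of the new intervention (Virtual Advisor) if the confidence interval lay completely above" −Δ; the mirror rule for the Peer Advisor arm uses +Δ. The effect size "is the standardized difference between the change in walking minutes/week over the 12-month intervention period".

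The section does not say which SD will standardize the difference at analysis, or how the mixed-effects estimate becomes d. It gives no criterion in minutes. On size, it states that "a sample of 112 per arm (224 total) would provide 80% power to demonstrate noninferiority between the two interventions".

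**The concern.** Cohen's d ordinarily takes its SD from the data being analyzed. A fixed Δ then tests the null that the Virtual Advisor deficit equals Δ × trial SD. The clinical null is a deficit of 30 minutes per week. The two agree at one SD only: 100 if Δ = .30, or 90 if Δ = .333. Replacing .30 by .333 moves that point but does not remove the dependence.

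The primary outcome is a four-week recall of walking (section 2.10), and recall error or outliers would raise its SD. With a margin in minutes, extra noise costs power. With a fixed margin in d, it widens the deficit accepted. If the SD is large enough, the Virtual Advisor could too often be called noninferior while losing the 30 minutes that the plan itself calls clinically meaningful. If the SD is small, a truly noninferior program could fail against a margin tighter than the clinical one.

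**Working it through.** **Inputs from section 2.15.** Clinical margin 30 min/week; planning SD 90; Δ printed .30 (30/90 = .333); 112 per arm; two-tailed 95% interval, so 2.5% one-sided for each claim.

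**The plan's own figure.** With no true difference, n per arm = 2(z_α + z_β)²(SD/margin)². One-sided 5%, 80% power and 30/90 give 2(1.645 + 0.842)² × 9 ≈ 111.3, so 112: the stated figure. Under the stated two-tailed 95% interval the same formula gives 142 per arm (.333) or 175 (.30). At 112 per arm, power is then about 70% or 61%.

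**Margin in minutes.** Margin = Δ × SD.

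**False noninferiority at a true deficit of 30 min/week.** The standard error of d is √(2/112) = 0.1336, taking the SD as already including clustering, as the plan says. The rate is Φ((Δ − 30/SD)/0.1336 − 1.96). Example, Δ = .30 and SD 120: (.30 − .25)/0.1336 = 0.374; 0.374 − 1.96 = −1.586; Φ = 5.6%.

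| SD of change | Margin, Δ = .30 | Rate, Δ = .30 | Margin, Δ = .333 | Rate, Δ = .333 |
|---|---|---|---|---|
| 90 | 27 min | 1.4% | 30 min | 2.5% |
| 100 | 30 min | 2.5% | 33.3 min | 4.4% |
| 110 | 33 min | 4.0% | 36.7 min | 6.6% |
| 120 | 36 min | 5.6% | 40 min | 9.1% |
| 130 | 39 min | 7.5% | 43.3 min | 11.7% |

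The rate passes 5% at an SD of about 116 (.30) or 103 (.333). Exact noncentral-t intervals give the same values, and simulation at SD 90, 120 and 140 agrees. With the 122 and 123 enrolled, the crossings are 115.5 and 102.4. If the standard error carries a further design effect of 1.25 to 2 (assumed), at 112 per arm they move to about 119–125 and 105–110.

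**The other direction.** With no true difference, power of the d rule is Φ(Δ/0.1336 − 1.96) = 61% (.30) or 70% (.333) at every SD. A 30-minute rule has Φ(30/(0.1336 × SD) − 1.96), which is 89% at SD 70.

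**Which SDs are plausible.** No SD of change is given. Table 1 gives a baseline SD of 91.6 for "Walking for exercise & leisure", one walking row in a sample screened for low activity. Assume a 12-month SD of 92, 110 or 130 and a correlation r of .3, .5 or .7. The change SD, √(91.6² + post² − 2r × 91.6 × post), then runs from 71 to 135. Over these nine combinations:

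- With Δ = .30, two exceed 5% (5.7% and 8.4%, both at r = .3), three lie between 2.8% and 4.9%, and four are below 2.5%.
- With Δ = .333, four exceed 5%.

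**A rule in minutes.** Simulated at a true deficit of 30 minutes, a 95% interval against −30 min/week gives 2.48%, 2.49% and 2.51% at SD 90, 120 and 140.

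**The case against.** The strongest reply is that section 2.15 never says d will be divided by the observed SD; the only SD it names is 90. If 90 is the fixed divisor there is no inflation: the simulated rate is 1.4–1.7% with Δ = .30 and about 2.5% with .333. This stands. Dividing by the trial SD is the ordinary meaning of Cohen's d, but here it is an inference, so the conclusion has to be conditional.

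It also stands that the printed rule is conservative at the plan's own SD: 27 minutes and 1.4%. A reader might infer from the d scale that the trial's false noninferiority rate is more than double the nominal 2.5%. The documents do not support that. With the printed Δ it requires both an observed-SD divisor and a change SD above about 116, some 29% over the planning value, and they report no SD of change.

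A third reply is that a standardized margin is a legitimate choice and the error rate is nominal against it. That does not answer the point, because the plan derives its Δ from 30 minutes per week. A rule that can drift from 30 minutes is not testing the criterion the plan sets.

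**Conclusion.** The point holds conditionally. The plan sets its clinical criterion in minutes and its decision rule in d, and leaves the divisor open. If d uses the observed SD, the effective margin is Δ × SD: too lenient above SD 100 (.30) or 90 (.333), too strict below. Over SDs of 90 to 130, false noninferiority at a 30-minute deficit runs from 1.4% to 7.5% with the printed Δ, or from 2.5% to 11.7% with .333.

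These figures assume 112 analyzed per arm, an SD that already includes clustering, and a two-tailed 95% interval. Neither leniency nor lost power is demonstrated. This is a cheap improvement that ties the primary conclusion to the plan's own criterion, not a shown failure of error control.

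**What to change.** In section 2.15, state the primary rule in minutes: the Virtual Advisor is noninferior if the two-tailed 95% confidence interval for the mixed-model difference (Virtual minus Peer) in 12-month change in walking lies wholly above −30 min/week; the Peer Advisor is noninferior if it lies wholly below +30. Keep SD 90 as a planning assumption only, and report Cohen's d descriptively.

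Fixing the divisor at 90 with Δ = 30/90 is the same rule in other units. Fixing it at 90 with the printed .30 would be a 27-minute rule.

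The change takes one or two sentences and no new data, since the model can estimate the difference in minutes. It has two costs. Power against 30 minutes at 112 per arm, with no true difference, is about 70% at SD 90, 61% at SD 100 and 46% at SD 120, and should be reported as such; 80% power would need 142, 175 and 252 per arm, and enrollment stands at 245 in total. At SD 90 the new rule is also slightly looser than the printed Δ implies (30 against 27 minutes), which the revised text should disclose.

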2.14. Randomization of community centers to study arms

Block randomization by county locale was used to assign ten community centers to the two major study arms. Centers were randomized in pairs by locale via coin toss by staff not involved in study assessment or intervention procedures. Allocation concealment was in place for each block of centers during the randomization process to minimize selection bias with respect to subsequent blocks. Assessment staff members are blinded to randomization assignment and masked to prior assessment data for each participant.

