3.1. Selection and description of study community centers

Ten community centers located in Santa Clara and San Mateo Counties, California with at least 20% Latino households (range = 21-55% Latino households) living within a one- to five-mile radius from the center were identified and expressed interest in serving as a study intervention site. These sites were block-randomized by locale to either the Peer or Virtual Advisor arms. Soon after recruitment, one center experienced unforeseen changes in its administration that disrupted center operations and precluded center participation in the study. To ensure comparable participant enrollment in each study arm, additional participants were enrolled at the remaining four community centers assigned to that intervention arm.

In each center, there were center staff who were willing to support the research team in reserving meeting space for clinical assessments, recruitment meetings, and, when relevant, Peer Advisor meetings. For the sites that received the Virtual Advisor, designated staff members were instructed on how to maintain the computer kiosk (i.e., refilling printer paper, providing minor technical support related to the computer such as making sure that it was switched on and that the touch screen remained clean, and contacting a member of the research team if needed.)

All participating community centers offered, as part of their usual activities, a nutrition program for older adults as well as nonphysical activity-oriented classes and activities, such as bingo, karaoke, and arts and crafts. Additionally, 89% offered weekly

physical activity classes and had at least one general computer available for older adults visiting their center.

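### The printed noninferiority margin (Δ = .30) does not follow from 30 min/week and SD 90 (.333), and 80% power at 112 per arm does not follow from the stated 95% confidence interval

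*Combined protocol and SAP*

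**What the plan says.** All the planning figures are in section 2.15. The decision rule is set by "Using a two-tailed 95% confidence interval on the effect size": the Virtual Advisor is noninferior if the whole interval lies above −Δ. The effect size "is the standardized difference between the change in walking minutes/week over the 12-month intervention period".

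The margin is explained as follows: "The noninferiority margin was based on a clinically meaningful difference, in one direction, between arms of 30 minutes walking/week", together with "a within-arm standard deviation of 90, accounting for clustering within centers ($\Delta=.30".

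On size, the section says "We calculated that a sample of 112 per arm (224 total) would provide 80% power to demonstrate noninferiority between the two interventions", and ties that figure to a method: "using a simple pre-post analysis". The planned analysis is a mixed-effects linear regression. Section 3.2 reports 122 participants enrolled in the Peer Advisor arm and 123 in the Virtual Advisor arm.

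The section does not give the alpha used for sizing, any baseline to 12-month correlation, or the assumed true difference. It does not say whether 90 is the SD of change or of a single time point. It also does not say which SD will be the denominator of the observed d.

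**The concern.** Δ decides the primary claim, and the section supports two values for it. A lower confidence limit between −.333 and −.30 passes on the derivation and fails on the printed figure. Because the rule is on a standardized scale with no named denominator, the same .30 can also stand for different numbers of minutes. A denominator chosen after the data are seen would move the margin.

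The stated power tells a reader how likely the trial was to show noninferiority if the two advisors are equally effective. If it is overstated, an inconclusive result may be read as evidence against the Virtual Advisor when the trial was simply too small for its own rule.

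**Working it through.** **Inputs from section 2.15:** raw margin 30 min/week; SD 90; printed Δ .30; two-tailed 95% interval, i.e. one-sided 2.5% against one margin (z = 1.960); power 80% (z = 0.8416); 112 per arm. Enrolled numbers are from section 3.2. **Assumed for steps 2 to 4, because not stated:** true difference 0, 90 is the SD of the analysed change, no baseline adjustment (relaxed in step 4), normal reference unless marked exact t.

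**1. Margin.** 30/90 = .333, which rounds to .33, not .30. In reverse, .30 × 90 = 27 min/week, and 30/.30 = 100. Moving the SD from 90 to 100 would need a variance factor of (100/90)² = 1.235. No such factor is given, and the text describes 90 as already allowing for clustering.

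**2. Reproducing 112.** n per arm = 2 × ((z_α + 0.8416)/d)². Power at 112 = Φ(d × 7.483 − z_α), where 7.483 = 1/√(2/112).

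| d | Error rate | n per arm (normal) | n per arm (exact t) | Power at 112 |
|---|---|---|---|---|
| .333 | one-sided 5% (z = 1.645) | 111.3 | 112 | 80.2% |
| .333 | 95% interval (z = 1.960) | 141.3 | 143 | 70.3% |
| .30 | one-sided 5% | 137.4 | 139 | 72.6% |
| .30 | 95% interval | 174.4 | 176 | 61.2% |

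For example, 2 × (2.8016/.3333)² = 141.3 and 2 × (2.8016/.30)² = 174.4. Of these four combinations, only the first gives 112. It uses neither the printed margin nor the error rate implied by the stated interval. Reading the SD as 100 with 30 min/week is again d = .30, so power at 112 stays at 61% (73% at one-sided 5%).

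**3. All enrolled, no dropout.** 1/√(1/122 + 1/123) = 7.826. Power is Φ(.3333 × 7.826 − 1.960) = 74% and Φ(.30 × 7.826 − 1.960) = 65%.

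**4. What would make 112 enough under the 95% interval.** Without adjustment, d = 2.8016 × √(2/112) = .374, or 33.7 min/week at SD 90. With covariate adjustment for baseline, n shrinks by (1 − r²). The correlation needed is √(1 − 112/141.3) = .46 at .333, or √(1 − 112/174.4) = .60 at .30.

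**5. If 90 is a single-time-point SD.** The SD of change is then 90 × √(2(1 − r)), which is 106.5 at r = .3 and 69.7 at r = .7. These values of r are illustrative. Power at 112 with the 95% interval:

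| Margin | r = .3 | r = .7 |
|---|---|---|
| 30 min/week (.333 × 90) | 56% | 90% |
| 27 min/week (.30 × 90) | 48% | 83% |

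Reaching 80% needs 2(1 − r) = 112/141.3, so r = .60, or 2(1 − r) = 112/174.4, so r = .68.

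**6. Minutes implied by .30.** At an SD of 80, 90, 100 or 110, .30 is 24, 27, 30 or 33 min/week. Table 1 gives baseline SDs for walking for exercise and leisure of 98.1 (Virtual), 81.4 (Peer) and 91.6 (all), so .30 would be 29.4, 24.4 or 27.5. These are baseline SDs, not SDs of change, and may not cover the full four-item outcome. They show only that the choice of denominator matters.

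**The case against.** The strongest reply is that the power shortfall is conditional. The section does not define the SD of 90, and Table 1's overall baseline SD of 91.6 makes a single-time-point reading plausible. Step 5 shows that true power could then be below 61% or above 80%. Baseline adjustment or the mixed model could also add precision. This stands as a limit on any claim about actual power. It does not restore the stated 80%: no correlation is documented, and the figure is tied to a simple pre-post analysis.

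A second reply is that .30 is the stricter value and so harmless. At SD 90 it is stricter. In general it is stricter than 30 min/week only if the standardizing SD is below 100; at SD 110 it is looser.

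A third is that 30 min/week, stated twice, was the intended margin, and that 112 reproduces from it. That is fair evidence, so the choice of primary margin is a judgement to be justified and documented.

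Finally, enrolment is complete, so restating power changes neither the design nor the verdict from the interval. That is correct: the power part is a reporting correction. The margin and its SD bear directly on the verdict.

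**Conclusion.** The section is wrong as written on two counts. The printed Δ of .30 is not 30/90. And 80% power at 112 per arm does not follow from the stated two-tailed 95% interval at either margin: it is about 70% (.333) or 61% (.30) under the step 2 assumptions. If the arms are truly equal, the chance of failing to show noninferiority is then about 30% or 39%, not 20%. Separately, the unnamed standardizing SD leaves the margin in minutes open.

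Confidence is high that the margin is mismatched and that the power does not follow from the stated inputs. It is only moderate for what the power actually is.

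A reader might infer three further things that the documents do not support:

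- That the false-noninferiority rate is inflated. At SD 90 the printed value is the more demanding one.
- That the trial was in fact sized at one-sided 5%. That combination reproduces 112, but the sizing alpha is not stated.
- That a specific lower power can be quoted for the small number of centers. Ten centers were randomized in pairs and one was lost (sections 2.14 and 3.1), which may lower power. But the plan specifies no degrees-of-freedom method, so any such figure would rest on a reference it does not contain.

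**What to change.** 1. Make the raw margin, the SD and Δ agree. Say whether 90 is the SD of change and whether it already includes the allowance for clustering.
2. Before outcomes are seen by arm, fix one primary margin in min/week with its d equivalent and a named SD. If no dated pre-outcome record shows the intended margin, use the more conservative of the two, 27 min/week (.30 at a fixed SD of 90), and report the verdict against 30 min/week as a sensitivity analysis. If outcomes have already been seen by arm, disclose the discrepancy and report both verdicts.
3. State the sizing alpha and any correlation used, and restate power for the two-tailed 95% interval from those inputs. If they cannot be found, give about 61% (.30) and 70% (.333) at 112 per arm with the step 2 assumptions. Note that the mixed model may raise power and that the small number of centers may lower it.

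The cost is a few sentences in section 2.15, one sensitivity analysis and a search for the sizing record; no new data are needed. The downsides are a less favourable stated power, unless a documented correlation supports more, and at SD 90 about 9 points less power at .30 than at .333 (65% against 74% with all enrolled).

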3.2. Study participants enrolled and recruitment sources

A total of 245 participants are enrolled in the primary trial (Peer Advisor arm: n = 122; Virtual Advisor arm: n = 123). Participant baseline demographic and health characteristics are summarized in **Table 1**. The study participants range in age from 50 to 87 years, and 79% are women, with about half of participants reporting being married or living with a partner. The predominance of women is common in such health promotion intervention studies, as is the reluctance of participants, especially from such lower-income communities, to report their household incomes. Forty-four percent of participants have high school or lower levels of education.

The highest recruitment yield (88.7% of enrolled subjects) was obtained from the geographically defined and demographically targeted bilingual mass mailings aimed at the Census blocks surrounding the community centers. The total number of targeted letters mailed describing the study and inviting individuals to contact the study team for more information was 107,930. The total cost of the targeted mailing recruitment strategy equaled approximately \$69,900.00.

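### The stated 80% power at 112 per arm does not follow from the plan's two-tailed 95% CI rule: at a true difference of 0 it is about 70% (margin 30/90) or 61% (printed margin .30)

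*Combined protocol and SAP*

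**What the plan says.** All the planning inputs are in Section 2.15.

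- **Decision rule.** "Using a two-tailed 95% confidence interval on the effect size" (Cohen's d), the plan will "demonstrate clinical noninferiority of the new intervention (Virtual Advisor) if the confidence interval lay completely above" the negative of the margin.
- **Scale.** Cohen's d is defined on the change in weekly walking minutes over 12 months.
- **Margin and SD.** The margin rests on 30 minutes of walking per week and a "within-arm standard deviation of 90, accounting for clustering within centers ($\Delta=.30". The 30 and the 90 each appear twice; the .30 appears once.
- **Power claim.** "We calculated that a sample of 112 per arm (224 total) would provide 80% power to demonstrate noninferiority". The section ties this figure to a comparison "between the two interventions using a simple pre-post analysis". The mixed-effects model is introduced after this, as the planned analysis.
- **Allowance for loss.** "Twenty-one additional participants were recruited to protect against loss to follow-up". Section 3.2 confirms the total: "A total of 245 participants are enrolled in the primary trial", 122 in the Peer Advisor arm and 123 in the Virtual Advisor arm.

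The section gives no other significance level, no assumed true difference between arms and no pre-post correlation.

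**The concern.** Requiring a two-tailed 95% interval to lie wholly above the negative margin is a one-sided test at 2.5%. A sample size computed at one-sided 5% is smaller, so quoting its power beside a 95% interval overstates the chance of success. The printed margin adds a second discrepancy: 30/90 is .333, not .30, and .30 at SD 90 is 27 min/week.

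This is the primary hypothesis. If noninferiority is not shown, a reader relying on 80% power would put the chance of a false negative at 20%. An unclear level and margin also leave room for dispute about the verdict, because a result near the boundary could pass on one reading and fail on another.

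**Working it through.** **Inputs.** From Section 2.15: 112 per arm, SD 90, difference 30 min/week, printed margin .30, two-tailed 95% CI (one-sided α = .025), simple pre-post comparison. From Section 3.2: 122 and 123 enrolled. Assumed: a true difference of 0. SD 90 is read as the SD of change, since d is defined on change. No further design effect is applied, since the plan says the SD already accounts for clustering.

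**Formulas** (normal approximation, d = standardized margin):

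- n per arm = 2(z₁₋α + z.₈₀)² / d²
- power = Φ(d / √(2/n) − z₁₋α)

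**Step 1: find what reproduces 112.** With α = .05 and d = 30/90, n = 2(1.645 + 0.8416)² / (1/3)² = 111.3, so 112. Power at 112 is Φ(2.494 − 1.645) = 80.2%. This matches the plan exactly, but it corresponds to a 90% CI.

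**Step 2: apply the plan's own rule.** With α = .025, √(2/112) = 0.1336.

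- d = 30/90: Φ(0.3333/0.1336 − 1.960) = Φ(0.534) = 70.3%
- d = .30: Φ(0.3000/0.1336 − 1.960) = Φ(0.285) = 61.2%

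| Margin | One-sided α | n per arm for 80% | Power at 112 per arm |
|---|---|---|---|
| 30/90 | .025 (95% CI) | 141.3, so 142 | 70.3% |
| .30 | .025 (95% CI) | 174.4, so 175 | 61.2% |
| 30/90 | .05 (90% CI) | 111.3, so 112 | 80.2% |
| .30 | .05 (90% CI) | 137.4, so 138 | 72.6% |

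Noncentral-t checks of the first two rows give 70.0% and 60.8%. With the printed .30, neither level gives 80% at 112.

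**Step 3: do the extra participants close the gap?** 224 + 21 = 245. If all 245 (122 + 123) were analysed with no loss, power under the 95% rule would be 74.2% (30/90) or 65.1% (.30).

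**Step 4: what would restore 80% at 112 under the 95% rule?** The standard error is 90 × 0.1336 = 12.03 min/week, and (1.960 + 0.8416) × 12.03 = 33.7. So 80% needs one of these:

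- a true Virtual Advisor advantage of 33.7 − 30 = 3.7 min/week (33.7 − 27 = 6.7 with .30); or
- an SD of 90 × 30/33.7 = 80.1 (90 × 27/33.7 = 72.1 with .30).

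The plan states neither.

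**Step 5: effect on the verdict (illustration at 112 per arm, SD 90, simple pre-post analysis).** The 95% half-width is 1.960 × 12.03 = 23.6, and the 90% half-width is 1.645 × 12.03 = 19.8. To show noninferiority, the observed difference (Virtual minus Peer, min/week) must be above:

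| | 95% CI | 90% CI |
|---|---|---|
| Margin 30 | −6.4 | −10.2 |
| Margin 27 (.30 × 90) | −3.4 | −7.2 |

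An observed difference of −5 would pass in three of these cells and fail in the fourth.

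**The case against.** **Nothing was miscalculated.** The 112 is right at one-sided 5% with 30/90, and the plan describes the clinically meaningful difference as being in one direction. It is fair to call this a conflict between the sizing level and the decision rule, not a slip of arithmetic. But that phrase describes the margin, and the only level stated is the two-tailed 95% interval. The 80% therefore still does not belong to the rule the trial will use.

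**SD 90 may be a single-time SD.** The plan does not call it an SD of change, and the enrolled baseline SD for leisure and exercise walking in Table 1 is 91.6. On that reading the SD of change is 90√(2(1 − r)), where r is the pre-post correlation. Power with margin 30 under the 95% rule is then 62% at r = .4, 70% at .5, 80% at .6 and 90% at .7. A baseline-adjusted analysis would give 78% at r = .4 and 82% at .5. So 80% is attainable with a suitable r. But the plan defines d on change and divides 30 by 90 to obtain the margin, so SD of change is its own reading, and it gives no r.

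**The .30 is probably a rounded 30/90.** This is likely, since only 30/90 leads to 112. The 70% figure is therefore the more probable one. The 61% still matters as long as .30 is the margin in print.

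**The limits in Step 5 are not the trial's limits.** This stands. The analysis will be a mixed model on data from nine remaining centers (Section 3.1). With 7 degrees of freedom (9 − 2), for example, the 95% half-width would be about 2.365 × 12.03 = 28.4. The limits show only that level and margin matter.

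**Enrolment is complete, and low power does not inflate false claims of noninferiority.** Both are true. They limit the remedy to reporting; they do not make the 80% correct.

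**Conclusion.** The concern holds. Under the plan's stated rule, power at 112 per arm falls short of the stated 80% by about 10 points (30/90) or 19 points (.30). The chance of failing to show noninferiority when the arms are truly equal is about 30% or 39%. Confidence is high that the 80% is unsupported as written. The specific figures rest on a true difference of 0, SD 90 as the SD of change with clustering already included, and the simple pre-post analysis to which the plan attaches its claim. The mixed model may recover some power, but without a correlation the gain cannot be stated. Sizing at one-sided 5% is the likely origin of 112; only the sponsor can confirm it. This should be fixed, although the decision rule itself remains valid.

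**What to change.** Keep the two-tailed 95% CI as the decision rule, and do not move to a 90% CI after the fact. Reconcile .30 with 30/90 and state one operative margin. Then replace the power statement with wording such as:

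> With 112 per arm, a two-tailed 95% CI, an SD of 12-month change of 90 min/week (accounting for clustering), a true difference of 0 and a simple pre-post analysis, power is about 70% [if the margin is 30/90] or about 61% [if .30]; 80% would need 142 or 175 per arm. The mixed model may add precision, but no gain is quantified.

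Ask the sponsor to confirm the significance level and true difference behind 112, and that 90 is the SD of change. If the sponsor reports different inputs, state them and recompute.

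The cost is wording and one confirmation from the sponsor. The quoted power becomes less favourable. No additional participants are needed.
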